5 STATISTICAL CONSIDERATIONS AND ANALYSES

5.1 General Considerations

All statistical procedures will be completed using SAS® version 9.4 or higher.

Continuous variables will be summarized using descriptive statistics, including the number of patients with non-missing value (n), mean, median, standard deviation (SD), minimum and maximum. “n” will be presented without a decimal point, minimum and maximum values will be presented with the same precision as in the database, mean and median will be presented with one more decimal place than the minimum and maximum, and SD will be presented with one more decimal place than the mean and median.

For categorical variables, summaries will include counts of patients (frequencies) and percentages. Percentages will be rounded to one decimal place. Descriptive summaries of change from baseline in categorical variables will be provided using shift tables, if applicable.

Day 0 is defined as the date when patients sign ICF.

No data imputation for any missing data will be done in this study.

5.2 Patient Dispositions

The number (%) of participants in enrolled population will be summarized. The number (%) of screen failures and reasons for screen failures will be provided in the screened population.

The number (%) of participants in the following categories will be provided:

- Participants who completed the study period as per protocol.
 - EOS is the date collected on “Study Participant Exit Form”.
- Participants who did not complete the study period as per protocol and main reason for study discontinuation (“Death”, “The study participant withdraws from the study”, “The study participant is being terminated by the investigator”, “The study participant transfers

USA

to another gastroenterologist”, “The study participant is lost to follow-up”, “Other reasons”).

5.3 Demographic and Baseline Characteristics

Demographic and baseline characteristics will be collected during the enrollment visits (See [Table 1](#)). Descriptive summaries of demographics and other baseline characteristics in the following categories will be presented for all enrolled population.

- Age
- Gender (“Woman”, “Man”, “Other”, “Prefer not to say”)
- Ethnicity (“Hispanic or Latino”, “Not Hispanic or Latino”)
- Race (“American Indian or Alaska Native”, “Native Hawaiian or Other Pacific Islander”, “Asian”, “Black or African American”, “White”, “Other”)
- Marital status (“Single”, “Married/Partnered”, “Divorced/Separated”, “Windowed”)
- Highest level of education (“High school, not completed”, “High school, completed”, “University, no degree”, “Associate or equivalent”, “Bachelor’s or equivalent”, “Master’s or equivalent”, “PhD or equivalent”)
- Annual household income
- Residence setting (“Rural”, “Suburban”, “Urban”)
- Current insurance coverage (“Insurance through a current or former employer or union”, “Insurance purchased directly from an insurance company”, “Medicare”, “Medicaid”, “TRICARE or other military healthcare”, “VA”, “Indian Health Service”, “Other type of insurance or health coverage plan”, “No insurance”)
- Current work status (“Full-time employed”, “Part-time employed”, “Retired”, “Unemployed, looking for work”, “Unemployed, unable to work”, “Student”)
- Height/weight (current weight, highest weight ever, unintentional weight loss)
- Family history of pancreatic disease, pancreatic cancer, pancreatic resection, celiac disease, and diabetes
- Current OTC herbal/nutritional supplements

USA

- The patient's chronic pancreatic etiology ("Toxic-Metabolic", "Metabolic", "Idiopathic", "Genetic", "Autoimmune", "Recurrent and severe acute pancreatitis", Obstructive, "Other")
- Evidence of suspected/confirmed EPI diagnosis ("Abnormal fecal elastase -1 test", "Clinical steatorrhea", "Vitamin deficiency", "Weight loss", "Pancreatic function testing", "Other")
- Clinical manifestations of EPI ("Diarrhea/loose stool", "Steatorrhea", "Abdominal pain", "Bloating", "Flatulence", "Unintentional weight loss/difficulty gaining weight", "Malnutrition", "Vitamin D deficiency", "Other vitamin/mineral deficiencies")

The baseline characteristics of abdominal pain, GI symptoms, dietary habits, health-related quality of life, depression/anxiety, PERT use and treatment satisfaction, and healthcare utilization will also be collected. Please see their individual sections below for detailed analysis.

5.4 Protocol Deviations

Protocol deviations for non-interventional, observational research are defined as those that may affect the rights or privacy of human subjects or the scientific integrity of the registry's objectives. If a protocol deviation occurs which meets this definition, the registry site will need to complete a protocol deviation form which will be sent to the sponsor.

Important protocol deviations, if applicable, will be identified prior to database lock. The number of patients with identified important protocol deviations will be summarized. Details on important protocol deviations will be provided in a listing.

5.5 PERT and other supplement/medication/therapies

Patients are considered as compliant if they are kept on PERT during the study. The eligible PERTs are listed in [Appendix A](#). If any patient answers "No" to the question "Do you take your

USA

enzymes everyday?” two times for two consecutive timepoints, , the patient is considered as noncompliant.

Descriptive summaries of the following categories will be presented, if applicable:

- Type of PERT (Creon®, Pancreaze®, Pertzye®, Viokase®, Zenpep®, Other)
- PERT Dose at initiation
- PERT Dose escalation (“Yes”, “Not Applicable”)
- PERT Dosing frequency per day
- Number of pills of PERT taken per day
- Habit when taking PERT (“With my meals only”, “With my snacks only”, “With my meals and snacks”, “Outside of my meals/snacks”, “Other”)
- PERT Route of administration (“Oral”, “Enteral feeding tube”, “Other”)
- Recommendation on how to take PERT (“Entire dose at the beginning of meal”, “Half before the meal and the other half during the meal”, “Entire dose 20 minutes before the meal”, “PERT should be taken with meals only”, “PERT should be taken with meals and snacks”, “Other”)
- Reason for switching to another PERT (“Efficacy”, “Dosing”, “Insurance coverage”, “Patient preference”, “Physician preference”, “Other”)
- How have enzymes been impacting the symptoms (“Greatly improved symptoms”, “Somewhat improved symptoms”, “Symptoms are unchanged”, “Somewhat worsened my symptoms”, “Greatly worsened my symptoms”)
- Type of vitamins and antioxidants (“Fat soluble vitamin supplement or repletion”, “Vitamin B 12 supplement”, “Zinc”, “Calcium”, “Probiotics”, “Other”)
- Type of pain medications (“Opioids”, “Simple analgesics”, “Tramadol”, “Non-steroidal anti-inflammatory drugs”, “Gabapentin”, “Cannabinoid”, “Other”)
- Type of neuromodulators (“Selective Serotonin Reuptake Inhibitors”, “Serotonin and Norepinephrine Reuptake Inhibitors”, “Tricyclic Antidepressants”, “Monoamine Oxidase Inhibitors”, “Atypical Antidepressants”, “Other”)

USA

- Type of Antidiarrheals (“Lomotil”, “Imodium”, “Other”)
- Type of other medication (“Insulin”, “Metformin”, “Other antidiabetic medications”, “Proton pump inhibitors”, “H2 blockers”, “Other”)
- Type of other therapies (“Dietician consultation”, “Other nutritional support/management”, “Cognitive behavioural therapy”, “Other”)

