3.2 Study Duration

This is a 5-year study with an anticipated first enrollment date of 01 April 2021. The total enrollment period will be 24 months in length and data collection and study close-out will take place 3 months prior to the anticipated study end date. The study duration from enrollment to study end is five (5) years.

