1 INTRODUCTION

The purpose of this Statistical Analysis Plan (SAP) is to provide detailed descriptions of the statistical methods, data derivations, and data displays for study protocol NES-EPI-100 “PAatient-CenTric Chronic Pancreatitis Registry” version 3.0 (13APR2021). The table of contents and templates for the Tables, Figures and Listings (TFLs) will be produced in a separate document.

All data analyses and generation of TFLs will be performed using SAS® version 9.4 or higher. The SAP will be finalized and signed off prior to locking the database.

USA

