5.15 Exploratory Analysis

Multivariate modeling will be employed to study both the EPI due to CP disease history and disease progression. The coefficients across the different models will be provided. P-value of exact F statistics test comparing the coefficients among different variables may also be provided.

Potential dependent variables are:

- Clinical manifestations of EPI (“Diarrhea/loose stool”, “Steatorrhea”, “Abdominal pain”, “Bloating”, “Flatulence”, “Unintentional weight loss/difficulty gaining weight”, “Malnutrition”, “Vitamin D deficiency”, “Other vitamin/mineral deficiencies”)
- How have enzymes been impacting the symptoms (“Greatly improved symptoms”, “Somewhat improved symptoms”, “Symptoms are unchanged”, “Somewhat worsened my symptoms”, “Greatly worsened my symptoms”)

USA

- The patient's chronic pancreatic etiology ("Toxic-Metabolic", "Metabolic", "Idiopathic", "Genetic", "Autoimmune", "Recurrent and severe acute pancreatitis", Obstructive, "Other")
- Evidence of suspected/confirmed EPI diagnosis ("Abnormal fecal elastase -1 test", "Clinical steatorrhea", "Vitamin deficiency", "Weight loss", "Pancreatic function testing", "Other")
- Abdominal pain pattern ("No pain", "Episodes of mild/moderate pain", "Constant mild/moderate pain", "Episodes of severe pain", "Constant mild/moderate pain plus episodes of more severe pain", "Constant severe pain")
- Health-Related Quality of Life
- Treatment compliance

Potential independent variables are:

- Type of PERT (Creon®, Pancreaze®, Pertzye®, Viokase®, Zenpep®, Other)
- Medical History
- Comorbidities (simultaneous presence of two or more diseases or medical conditions)
- PERT Dose at initiation
- PERT Dose escalation
- Recommendation on how to take PERT ("Entire dose at the beginning of meal", "Half before the meal and the other half during the meal", "Entire dose 20 minutes before the meal", "PERT should be taken with meals only", "PERT should be taken within meals and snacks", "Other")
- Reason for switching to another PERT ("Efficacy", "Dosing", "Insurance coverage", "Patient preference", "Physician preference", "Other")

Healthcare utilization rate may be calculated based on

- Number of healthcare providers
- Number of ER visits

USA

- Number of tele health visits
- Hospitalizations and length of stay
- Number of sick days, if employed in the past 6 months

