Potential confounders will be explored for predicting outcomes with the registry data. If any confounding is identified, statistical procedures such as stratified analysis, multivariable analysis, and/or sensitivity analysis may be employed as appropriate for that confounder and outcome.

USA**6 APPENDICES****6.1 Appendix A – Eligible PERT**

Drug Type	Non-Proprietary Name	Brand Name
Pancreatic Enzyme Replacement Therapy	Pancrelipase	Zenpep®
	Pancrelipase	Creon®
	Pancrelipase	Pancreaze®
	Pancrelipase	Pertzye®
	Pancrelipase	Viokase®

USA

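### The SAP 5.5 noncompliance label has no common window or censoring, so any proportion built on it rises with length of follow-up, which differs by plan (minor)

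*SAP*

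**What the plan says.** SAP 5.5 has two sentences on compliance. The first reads "Patients are considered as compliant if they are kept on PERT during the study". The second makes a participant noncompliant if the daily-enzyme question is answered 'No' "two times for two consecutive timepoints". Neither gives an interval, a minimum number of answers, a rule for reversal, or a rule for participants who leave early. The output list that follows does not include a compliance rate, and SAP 1 says that "templates for the Tables, Figures and Listings (TFLs) will be produced in a separate document".

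SAP 5.15 (Exploratory Analysis) lists "Treatment compliance" as a potential dependent variable. Its potential independent variables include "PERT Dose escalation" and "Reason for switching to another PERT". On confounding it says "Potential confounders will be explored for predicting outcomes with the registry data"; follow-up time is not named.

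On timing, Protocol 3.2 describes a five-year study and says "The total enrollment period will be 24 months in length", with data collection closing three months before study end. Protocol 6.3.4 collects PERT use every three months. Protocol 6.4 makes the end of registry data collection an exit reason, and the Schedule of Assessments gives five years as a maximum. SAP 5.1 rules out imputation.

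**The concern.** A label that is triggered once and has no stated way back can only become more frequent as answers accumulate. Two participants who behave identically have different chances of being called noncompliant if one enrolled earlier or stayed longer. A participant with fewer than two answers can never meet the two-'No' rule and is compliant by default, since missing answers are not imputed.

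This is the SAP's only definition of treatment compliance, which is Aim 4, and Protocol 11 says that compliance will be examined for each of the models. Two uses are exposed: any proportion computed from the label, and an SAP 5.15 model with compliance as outcome and a covariate that also accumulates with time under observation.

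**Working it through.** The documents give no compliance rate, so there is no planned figure to reproduce.

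**Follow-up (Protocol 3.2, 6.3.4).** First enrolled: 60 − 3 = 57 months, 57/3 = 19 answers after Day 0. Last enrolled: 60 − 24 − 3 = 33 months, 33/3 = 11 answers. If closeout is at month 60, as the synopsis can be read, these become 20 and 12. The same counts arise if Day 0 is included on the first reading.

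**Probability of the label.** Assume a chance p of 'No' at each answer and every form completed. Let a = no run yet and last answer not 'No', b = no run yet and last answer 'No', c = labelled. Start at a = 1, b = c = 0 and update:

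a′ = (a + b)(1 − p); b′ = a·p; c′ = c + b·p.

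With p = 0.2, c is 0 after one answer, 0.04 after two and 0.04 + 0.16 × 0.2 = 0.072 after three. It reaches 0.298 after 11 and 0.469 after 19. The odds ratio is (0.469/0.531)/(0.298/0.702) ≈ 2.1.

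For between-person variation, let p follow a Beta(0.2s, 0.8s) distribution; the probability is 1 − Σₖ C(n−k+1, k) E[pᵏ(1−p)ⁿ⁻ᵏ].

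| Assumption (mean 20% 'No') | 11 answers | 19 answers | Odds ratio | 12 v 20 answers |
|---|---|---|---|---|
| Independent answers | 29.8% | 46.9% | 2.1 | 32.2 v 48.8% |
| Beta, s = 5 | 30.9% | 41.2% | 1.6 | 32.5 v 42.1% |
| Beta, s = 1 (strong variation) | 27.5% | 31.9% | 1.2 | 28.3 v 32.3% |

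The gap is zero if noncompliance is a fixed trait and everyone gives at least two answers. For other values of p with independent answers, 11 versus 19 answers gives 2.4 v 4.2% (p = 0.05), 8.9 v 15.3% (0.10) and 54.0 v 75.0% (0.30).

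**Dose-escalation association.** Suppose escalation is unrelated to compliance and recorded as ever having occurred. Entry t is uniform over 0 to 24 months, and follow-up f = min(57 − t, exponential exit time). Answers n = floor(f/3), six-monthly visits m = floor(f/6), and P(escalated) = 1 − (1 − h)^m. Label and escalation are independent given f, so any odds ratio other than 1 comes from shared follow-up. Exit rates and h are assumptions. Triples are independent / s = 5 / s = 1.

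| Escalation timing | No early exit | 10% exit per year | 20% exit per year |
|---|---|---|---|
| h = 10% at every visit | 1.05 / 1.03 / 1.02 | 1.47 / 1.39 / 1.27 | 1.85 / 1.71 / 1.50 |
| h = 10%, first two visits only | 1.00 | 1.14 / 1.13 / 1.12 | – |
| h = 30%, first two visits only | 1.00 | 1.22 / 1.21 / 1.19 | – |

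**Fewer than two answers.** About 5.1% of participants at 10% exit and 10.5% at 20%; counting Day 0 roughly halves this, to 2.6% and 5.5%. Excluding them and keeping the whole-study label still leaves 1.29 / 1.22 / 1.12 at 10% exit and 1.47 / 1.36 / 1.19 at 20% (h = 10% at every visit).

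**Check of the fix.** At a given assessment, everyone still at risk has had the same number of assessments and visits, so follow-up length no longer links escalation to the event. In simulation (600,000 participants per scenario, h = 10% at every visit, random exit of 0, 10 or 20% per year), the odds ratio of first event by prior escalation, stratified by assessment number, lay between 0.985 and 1.012.

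**The case against.** The strongest reply is that little depends on this label. SAP 5.15 is exploratory, its variables are only potential, no hypothesis test rests on compliance, and no compliance rate is listed. The confounder sentence permits stratified, multivariable and sensitivity analyses, and SAP 5.5 also describes PERT use through dosing frequency, pills per day and meal habit. This stands as a reason for low severity. It does not remove the defect: the confounder sentence is generic, and adjustment cannot make a participant with one answer evaluable.

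Three stronger readings are tempting but unsupported.

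- A reader might infer that staggered enrollment by itself biases the compliance models. For dose escalation it hardly does (1.02 to 1.05). The larger odds ratios of 1.2 to 2.1 compare first with last enrolled, and entry date is not a listed covariate.
- A reader might extend the argument to "Reason for switching to another PERT". That variable is a nominal reason that exists only for participants who switched, not a cumulative ever-switched indicator, so no claim is made for it.
- A reader might infer that the study will report a distorted rate. The documents do not show that a rate will be reported.

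The size of the escalation effect is also fairly challenged. The documents give neither exit rates nor the timing of escalation, and early escalation cuts the false odds ratio at 10% exit to about 1.1 to 1.2.

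**Conclusion.** The point holds as a minor one. As written, the label depends on how long a participant is observed. The direction follows from the definition whenever answers vary over time; the size rests on assumed inputs. For a proportion, the contrast between shortest and longest planned follow-up is 29.8% versus 46.9% at one extreme and 27.5% versus 31.9% under strong between-person variation, and none for a fixed trait with at least two answers each. For the SAP 5.15 compliance model, distortion of the dose-escalation association comes mainly from early exit, about 1.1 to 1.5 at 10% per year, and only if escalation is recorded cumulatively. Covariates unrelated to follow-up are not affected by this mechanism.

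**What to change.** Keep the two-consecutive-'No' event, but analyse it as time to first event from enrollment, censored at the last completed assessment, or over a common window (for example 12 or 33 months) with censoring for early exit. Use this for any reported compliance summary and for the SAP 5.15 compliance model, entering dose escalation as status before each assessment. Do not rely on the whole-study binary label with only those lacking two answers excluded: the residual false odds ratio is about 1.1 to 1.3 at 10% exit and 1.2 to 1.5 at 20%, when escalation is equally likely at every visit.

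Reconcile the two SAP 5.5 sentences: state the data source for being kept on PERT, whether consecutive refers to scheduled or completed timepoints, and whether Day 0 counts, given that Protocol 5.2 admits participants newly prescribed PERT at enrollment.

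The cost is a small derivation change on data already collected. The figure can move either way: with independent answers at 20%, the whole-study label gives 37.7%, 30.9% and 25.1% at 0, 10 and 20% exit per year, against a 33-month cumulative incidence of 29.8% in all three. Censoring assumes that exit is unrelated to compliance. That is doubtful, because Protocol 6.4 ties loss to follow-up to missed assessments on the same portal. Report it as a limitation, with a sensitivity analysis.

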The benefits in treatment of EPI have led to practice guideline recommendations for the use of PERT in patients with CP, pancreatic cancer, and pancreatic surgery (Sabater et al., 2016). However, studies suggest that the majority of patients are either not treated or treated with inadequate dosages. In a European survey study of patients with EPI due to CP or pancreatic cancer, one-quarter of patients took three or fewer capsules a day and more than two-thirds of patients reported ongoing symptoms of steatorrhea (Sikkens et al., 2012b). Similarly, in a Dutch national survey of patients with CP and EPI, the median initiating daily dosage was suboptimal (four capsules daily, 25,000 USP units of lipase each), and a majority of patients reported ongoing gastrointestinal symptoms of EPI including steatorrhea and weight loss (Sikkens et al., 2012a). More recently, in a US population-based analysis, 6.5% of patients with CP received any testing for EPI, 30.4% received a prescription for PERT, and only 10% received a minimally effective dose (Forsmark et al., 2017a). Likewise, in a similar analysis of patients with pancreatic cancer, only 1.9% of patients had testing for EPI and 22% received a prescription for PERT, with only 5.5% receiving an adequate dose (Forsmark et al., 2017b). Ultimately, these studies highlight that diagnostic testing is rarely performed, treatment with PERT is infrequent, and, if utilized, the dosage amounts are generally inadequate.

In order to better study the disease journey and the effectiveness and safety of available therapies for EPI, databases and registries are needed. To date, however, there have only been a few observational studies conducted on EPI. These existing databases are limited as they lack measures that could advance the understanding of the disease, comorbidities, disease progression, risk and/or mitigating factors. In addition, these studies do not provide a comprehensive assessment of existing treatments. This observational study with geographical representation across the United States will be well positioned to address the above-mentioned issues by collecting a comprehensive set of real-world data around disease and treatment outcomes.

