7.5.6 PERT Use and Treatment Satisfaction

Study participants will be asked whether PERTs have an impact on their symptoms (greatly improved symptoms to greatly worsened symptoms) and how they are taking the PERTs on a typical day (i.e., frequency, number of pills, and with/without meals and snacks). Treatment satisfaction related to PERTs will be measured with the Treatment Satisfaction Questionnaire for Medication – 9 items (TSQM-9). The TSQM-9 is a global satisfaction scale used to assess the overall level of participant's satisfaction or dissatisfaction with their medications. It comprises 9 items on 3 subscales: effectiveness, convenience and global satisfaction. The scores are computed by adding items for each domain, i.e., items 1 – 3 for effectiveness, items 4 – 6 for convenience and items 7 – 9 for global satisfaction (Bharmal et al., 2009). The lowest possible score (1 for each item and 3 for all 3 subscales) is subtracted from the composite score and divided by the greatest possible score range. The greatest range is $(7-1) \times 3$ items = 18 for the effectiveness and convenience, and $(5-1) \times 3$ items = 12 for global satisfaction. This provides a transformed score

between 0 and 1 that is then multiplied by 100; scores for the domains range from 0 (extremely dissatisfied) to 100 (extremely satisfied), with higher scores indicating greater satisfaction.

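### SAP 5.5 measures daily-use persistence but calls it compliance, and its two sentences place some participants in both classes or in neither

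*SAP*

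**What the plan says.** SAP 5.5 holds the only definition of compliance in either document, and it has two sentences. The first: "Patients are considered as compliant if they are kept on PERT during the study". The second rests on one yes/no item, whether the participant takes the enzymes every day. A No given "two times for two consecutive timepoints, , the patient is considered as noncompliant". I read that as No on two 3-monthly forms in a row.

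The same section then lists items for descriptive summary only. They include "Habit when taking PERT" (meals only, snacks only, both, outside meals and snacks, other), "Number of pills of PERT taken per day", dosing frequency, and "Recommendation on how to take PERT" (six options covering timing, meals only, meals and snacks, and other). Protocol 7.5.6 confirms that participants report "how they are taking the PERTs on a typical day (i.e., frequency, number of pills, and with/without meals and snacks").

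Compliance is Specific Aim 4 (Protocol 2, SAP 2.1). Protocol 11 says it will be examined in each of the models, and SAP 5.15 lists it as a potential dependent variable.

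**The concern.** PERT is taken around eating, and the registry records both what was advised and what was done. A reader of Aim 4 would expect compliance to compare the two. The rule compares neither; it asks whether the participant stayed on PERT and took it daily.

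Two things are at stake. First, the label does not mean what it says. Participants who take PERT daily but not as advised are grouped with those who follow the advice, and participants who stop because their prescriber stopped PERT can be grouped with those who do not follow it. Second, the two sentences are not complements, so two programmers could classify the same participant differently and both be faithful to the SAP.

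**Working it through.** The documents give no compliance figure, so there is none to reproduce. The main check applies the two sentences literally to specific cases.

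| Case | Sentence 1 (kept on PERT) | Sentence 2 (No at two consecutive timepoints) | Result |
|---|---|---|---|
| A. Advised meals and snacks; takes PERT every day with snacks only | met | not met | compliant |
| B. Prescriber stops PERT; item still asked; answers No from then on | not met | met | noncompliant |
| C. Prescriber stops PERT at the last timepoint, or item no longer asked after the stop | not met | not met | undefined |
| D. Off PERT for one quarter, then back on it; one No | not met | not met | neither class |
| E. Still on PERT; No on two forms in a row | met | met | both classes |

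Case A follows directly from the text. Cases B and C follow from applying the rule; the SAP does not mention prescriber-directed stops. Cases D and E show the gap and the overlap.

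**Side check: dependence on length of follow-up.** Inputs are the 5-year study, 24-month enrollment, data collection ending 3 months before study end, and 3-monthly forms (Protocol 3.2 and 6.3.1).

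- Longest follow-up: 60 − 3 = 57 months; 57 / 3 = 19 follow-up forms.
- Shortest without early exit: 57 − 24 = 33 months; 33 / 3 = 11 forms.
- With alternating answers, the most No answers without a consecutive pair is (n + 1)/2 for odd n: 6 of 11, or 10 of 19.

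Let p be the chance of No on any form, with answers independent and every form completed (all assumed). Let a be the probability of no pair so far with the last answer Yes, b of no pair so far with the last answer No, and c of a pair having occurred. Start at a = 1, b = c = 0, and at each form set a' = (a + b)(1 − p), b' = a·p, c' = c + b·p. The final c is the chance of ever being labelled noncompliant.

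| Assumed p | 11 forms | 19 forms |
|---|---|---|
| 5% | 2.4% | 4.2% |
| 10% | 8.9% | 15.3% |
| 20% | 29.8% | 46.9% |
| 30% | 54.0% | 75.0% |

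Participants with the same behaviour are thus more likely to be labelled noncompliant the longer they are followed. The values of p are illustrative. The check supports a per-timepoint rule and does not estimate the registry's compliance rate.

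**What the listed items allow.**

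- Habit records meals and snacks but no timing within or before a meal. Of the six recommendation options, only meals only and meals and snacks can be compared with it; three are timing rules and one is other.
- For amount, SAP 5.5 lists dose at initiation and whether it was escalated, but not a currently recommended pill count.
- It lists reasons for switching PERT, but not for stopping it.
- The Investigator records current treatment since the last visit about every 6 months (Protocol 6.3.4), which gives prescribing status.

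**The case against.** The strongest case on the other side is that this is largely a matter of labelling in a descriptive registry. Frequency, pills, habit and recommendation are each summarised in SAP 5.5, so low intake would be visible. Protocol 11 already warns of recall bias, and compliance enters only exploratory models. A full concordance measure cannot be built from the listed items. Using concordance as an outcome while the recommendation is a predictor, as SAP 5.15 would allow, builds the predictor into the outcome.

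Most of this stands, and it limits both the severity and the fix. It does not remove the point. Separate summaries of advice and habit do not show who departs from their own advice, and the overlap and gap between the two sentences remain whatever the label.

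A stronger reading is tempting. The Protocol's Background cites a European survey in which "one-quarter of patients took three or fewer capsules a day". A reader might apply that to the target of 400 (0.25 × 400 = 100) and infer that the compliance rate is overstated by up to 25 percentage points. The documents do not support this:

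- The survey figure is for low intake, not intake below what was recommended. Someone advised to take three capsules who takes three is following the advice, and three capsules can cover three meals under a meals-only recommendation.
- The next survey cited there gives a median starting dosage of four capsules a day, so low prescribing is a competing explanation.
- The survey included pancreatic cancer, which this registry excludes.

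**Conclusion.** The point holds as a definition problem. The SAP 5.5 rule measures daily-use persistence, misdescribes participants who take PERT daily but not as advised, ordinarily labels a prescriber-directed stop as noncompliance, and is neither exhaustive nor mutually exclusive. This rests on the wording alone. The result for prescriber stops also assumes that the item is still asked and the stop is not at the last timepoint; otherwise status is undefined.

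The size of the error in the compliance rate cannot be derived from the documents, and nor can its direction. A reader might infer that the rate must be too favourable, but case A raises it and case B lowers it, with no frequency given for either. A reader might also infer that associations with outcome are diluted. That would need misclassification unrelated to outcome, which nothing in the documents establishes.

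No sample size, power or alpha figure is affected. The change should be made before database lock because Aim 4 depends on the variable.

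**What to change.** Change SAP 5.5 and 5.15 as follows. These are analysis derivations and imply no clinical rule.

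1. Replace the two sentences with one rule that gives each participant exactly one class at each 3-month timepoint, and label it daily-use persistence. State how a missing answer is classed, since SAP 5.1 rules out imputation.
2. Evaluate it only at timepoints where the Investigator's current-treatment record shows PERT is prescribed. Report participants no longer prescribed PERT separately as off PERT, with the reason if the eCRF captures it, and not as noncompliant. Because that record is about 6-monthly and the forms are 3-monthly, say which record governs the forms between visits.
3. Add a separate meal/snack concordance measure. Compare reported habit with the latest recorded recommendation where that is meals only or meals and snacks, and report all others as not classifiable.
4. In SAP 5.15, use both measures where treatment compliance is listed. When concordance is the dependent variable, leave the recommendation out of the predictors.

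The cost is a SAP revision and some programming; the core uses items already listed. The downside is coverage. Participants with only a timing-type or other recommendation are not classifiable for concordance, and pill-count concordance is possible only if the eCRF records the currently prescribed amount.
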